## **VARIABLES EVALUATED**

The main variable will be the measurement of pain intensity according to the NRS at different times: preoperative and at the 1st, 2nd, 12th and 24th postoperative hours. As secondary variables, postoperative opioid requirements will be assessed in the form of intravenous morphine, measured in mg (only during the 2 hours of the patient's stay in the Postanesthesia Care Unit), and tramadol (mg) up to 24 hours postoperatively.

The degree of sensory block will be also assessed by a cold sensitivity test with a cotton swab dipped in cold water applied to the skin of the upper third of the arm, which will be graded with a sensitive scale going from 0 to 2 (2 being normal sensitivity to cold, 1 hypoesthesia and 0 anesthesia). The degree of motor block upon arrival at the PACU will be assessed by the movement of the arm using a simple numerical scale (0 = cannot raise the extended arm  $> 45^\circ$  and 1 = can raise the extended arm  $> 45^\circ$ ), the ease of performance of the corresponding anesthetic technique by the anesthesiologist using a simple verbal scale (easy/medium difficulty/difficult), the appearance of adverse effects (postoperative nausea and/or vomiting, hematoma, pruritus, urinary retention), the degree of patient satisfaction (very satisfied, satisfied or dissatisfied) and the notification of complications related to the anesthetic techniques performed.

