## **STATISTICAL ANALYSIS PLAN**

Continuous quantitative variables will be expressed as mean and standard deviation and the results will be contrasted using the Student's T test if normality criteria will be met, failing which they will be expressed as median and range and contrasted using the Mann Whitney's U. The qualitative variables will be expressed in absolute numbers and relative frequencies and the results of both groups will be contrasted using the Chi square. In addition, Fisher's test will be applied when necessary. Normality tests will be conducted for all continuous quantitative variables. The Kruskal-Wallis technique will be also employed with post-hoc application of the Bonferroni test for the analyses. The data will be processed using SPSS software version 19.0 (IBM Corporation, Armonk, NY, USA), assuming a p-value below 0.05 as significant.

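### Three secondary outcomes with ordered levels have no ordinal test; the only rule that fits them, chi-square or Fisher, ignores the order and loses power to detect a shift along the scale

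*Combined protocol and SAP*

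**What the plan says.** VARIABLES EVALUATED defines three secondary outcomes with three ordered levels each:

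- Sensory block to cold, "graded with a sensitive scale going from 0 to 2", with the levels defined as "2 being normal sensitivity to cold, 1 hypoesthesia and 0 anesthesia".
- Ease of the technique, rated by the anesthesiologist in three verbal grades from easy to difficult.
- Satisfaction: "the degree of patient satisfaction (very satisfied, satisfied or dissatisfied".

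The GOALS section lists all three among the secondary objectives.

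The STATISTICAL ANALYSIS PLAN has two classes of variable. The first rule begins "Continuous quantitative variables will be expressed as mean and standard deviation" and leads to the t test or, without normality, to Mann-Whitney U. The second covers qualitative variables, reported as counts and relative frequencies, and states that "the results of both groups will be contrasted using the Chi square". It then adds "In addition, Fisher's test will be applied when necessary". A further sentence reads "The Kruskal-Wallis technique will be also employed with post-hoc application of the Bonferroni test for the analyses" and names no outcome. The threshold is given as "assuming a p-value below 0.05 as significant", without saying one- or two-sided. No rule mentions ordinal variables.

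**The concern.** The two verbal scales cannot be continuous quantitative variables, so the qualitative rule is the only one that fits them. The 0 to 2 sensory grade most naturally follows, because it is not continuous, but the plan does not classify it.

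In a table of two groups by three levels, Pearson chi-square and Fisher's test give the same p-value however the levels are ordered. The clinical question is ordered: does one technique give a better or worse grade than the other? A test on 2 degrees of freedom spreads its sensitivity over patterns that do not answer that question, and so has less power for the one that does. JUSTIFICATION OF SAMPLE SIZE says that no calculation will be done, so nothing secures power for these outcomes.

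There is also a gap in the specification. With a rank test named but attached to no outcome, an analyst could defend either chi-square or Kruskal-Wallis for the same variable after seeing the data.

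**Working it through.** **Inputs from the documents.** Two groups; three outcomes with three ordered levels; chi-square or Fisher for qualitative variables; threshold 0.05. The documents state no power figure, so there is none to reproduce.

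**Assumptions.** Two-sided testing; 1:1 allocation; 20 to 100 patients per group; level shares in one group of 33/33/33%, 60/30/10% or 75/20/5%; a proportional-odds shift with odds ratio (OR) 2, 2.5 or 3; independent patients.

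**Step 1: the two tests on one illustrative table.** Take 30 per group, with counts 12/10/8 and 6/9/15 on levels 0/1/2.

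- Chi-square: column totals are 18, 19 and 23, so expected counts per group are 9, 9.5 and 11.5. The statistic is 2 × (3²/9 + 0.5²/9.5 + 3.5²/11.5) = 2.000 + 0.053 + 2.130 = 4.183 on 2 df, p = 0.123. Reordering the levels changes nothing.
- Mann-Whitney: U = 321 against a null mean of 30 × 30/2 = 450, a difference of 129. The tie-corrected variance is (900/12) × [61 − (5814 + 6840 + 12144)/(60 × 59)] = 75 × 53.995 = 4049.6. Then 129²/4049.6 = 4.109 on 1 df, p = 0.043.
- Kruskal-Wallis on the same two groups gives 4.109, p = 0.043, identical to Mann-Whitney.

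The statistics are nearly equal; the difference in p comes from the second degree of freedom. The table was chosen to show the mechanism and says nothing about how often the two tests disagree.

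**Step 2: how a shift is built.** A proportional-odds shift divides each cumulative odds by the OR. From 60/30/10% with OR 2.5, the cumulative odds 1.5 and 9 become 0.6 and 3.6. The cumulative shares are 0.6/1.6 = 0.375 and 3.6/4.6 = 0.783, so the levels are 37.5/40.8/21.7%.

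**Step 3: simulated power** (40,000 tables per setting), chi-square vs tie-corrected Mann-Whitney, OR 2.5:

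| Assumed level shares | n per group | Chi-square | Mann-Whitney | Gain (points) |
|---|---|---|---|---|
| 33/33/33% | 30 | 36.9% | 46.4% | 9.5 |
| 33/33/33% | 50 | 57.5% | 68.1% | 10.6 |
| 33/33/33% | 100 | 87.8% | 93.2% | 5.4 |
| 60/30/10% | 30 | 35.1% | 44.8% | 9.7 |
| 60/30/10% | 50 | 55.4% | 66.2% | 10.8 |
| 60/30/10% | 100 | 86.7% | 92.4% | 5.7 |
| 75/20/5% | 30 | 29.3% | 38.9% | 9.6 |
| 75/20/5% | 50 | 48.3% | 58.5% | 10.2 |
| 75/20/5% | 100 | 79.8% | 87.6% | 7.8 |

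Over all settings with OR 2 to 3 and n from 20 to 100, the gain runs from about 2 points (33/33/33%, n = 100, OR 3: 96.4% vs 98.4%) to about 11 points (75/20/5%, n = 30, OR 3: 42.0% vs 53.4%).

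**Step 4: error rate under no difference.** Chi-square 3.4% to 5.2%; Mann-Whitney 4.7% to 5.1%.

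**Step 5: large-sample check.** For 80% power at 0.05 the noncentrality must be 7.85 on 1 df and 9.63 on 2 df. The ratio is 9.63/7.85 = 1.23, so the 2-df test needs about 23% more patients if the ordered test captures the whole difference. Where the 1-df test has 80% power, the 2-df test has 71%.

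**Step 6: a case against the rank test.** With 40/20/40% vs 25/50/25% and 50 per group, both groups have a mean grade of 1. Chi-square has 83% power and Mann-Whitney 6%.

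**The case against.** A reader might infer that the plan commits all three outcomes to an order-blind test, that this brings no benefit, and that the analysis could not show which technique did better. The documents do not support any of these.

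- **Commitment.** The plan never classifies these outcomes. Sending the sensory grade to chi-square is an inference, and the Kruskal-Wallis sentence could be meant for them. With two groups that would be the same test as Mann-Whitney. What stands is that no outcome is attached to it, and a Bonferroni post-hoc step has no role in a comparison of two groups.
- **No benefit.** Chi-square assumes no consistent shift and finds non-monotone differences that a rank test misses (step 6). That is a real but small cost. More middle grades and fewer at both extremes is not a better-or-worse difference on any of these scales.
- **No direction.** The chi-square p-value has none, but the planned counts and frequencies let the reader see it in each table.

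Three limits on the remedy also stand. First, every power figure rests on assumptions, and proportional odds is a setting that favours ordered tests. Second, the PROTOCOL section assigns patients according to the anesthesiologist doing the block, and the anesthesiologist rates ease. Those ratings may cluster by operator and be confounded with group, and an unadjusted rank test does nothing about that. Third, STUDY TYPE calls the cohorts paired; if patients really are matched, Mann-Whitney ignores the matching just as chi-square does.

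**Conclusion.** The point holds as a minor one about efficiency and specification. Both tests keep the error rate near or below 5% when patients are independent, so chi-square here is valid, only less sensitive to the difference of interest. The outcomes are secondary, no power is claimed for them, and the pain analysis is untouched.

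The loss is roughly 2 to 11 points of power. It is smallest where power is already very high and about 10 points at 30 to 50 per group with OR 2.5. Group size, allocation ratio, level shares, odds ratio and the proportional-odds form are all assumed, so the range shows the order of magnitude and does not predict what this study would lose.

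**What to change.** Add one sentence to the STATISTICAL ANALYSIS PLAN: for sensory block, ease of technique and patient satisfaction, the groups are compared with the tie-corrected Mann-Whitney U test, and counts and percentages are reported for each level. Optionally add a proportional odds ratio with its 95% confidence interval, which gives both direction and size. Keep chi-square and Fisher for binary and unordered variables such as motor block and adverse effects. State what Kruskal-Wallis with Bonferroni is for, or delete it.

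The cost is a line of text. No new data are needed, and Mann-Whitney is already in the plan. The price is lower power against non-monotone differences, which the per-level percentages would still display. Operator confounding and clustering need separate treatment, above all for ease of technique.

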### **GOALS:**

- **Main objective**

The measurement of pain intensity according to the NRS at different times: preoperative and at the 1st, 2nd, 12th and 24th postoperative hours.

- **Secondary objectives**

Postoperative opioid consumption and comparison of total cumulative consumption between the two groups.

It will also evaluated the degree of sensory and motor block, the easy of performance of the anesthetic technique, the degree of patient satisfaction and the record of short-term complications (first 24 hours post-intervention): hematoma, pruritus, nausea and/or vomiting.

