## **JUSTIFICATION OF SAMPLE SIZE**

Because no work of this nature has been carried out previously, a sample size calculation will be not performed and all patients who underwent surgery in the 12 months that the study data collection will last were consecutively included in the study.

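### Kruskal-Wallis with Bonferroni is planned without a target: it is redundant between the two blocks and far too conservative if run across the repeated NRS times, and it leaves the main group comparisons uncorrected

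*Combined protocol and SAP*

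**What the plan says.** The STATISTICAL ANALYSIS PLAN sends normally distributed continuous variables to Student's t. Otherwise they are "failing which they will be expressed as median and range and contrasted using the Mann Whitney's U". Qualitative variables go to Chi square, or Fisher where needed. The section then adds: "The Kruskal-Wallis technique will be also employed with post-hoc application of the Bonferroni test for the analyses". It does not say which variable, factor or time points this covers. The significance rule is "assuming a p-value below 0.05 as significant", and no other multiplicity adjustment appears.

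The study has two block groups. The opioid objective under GOALS, for example, is a "comparison of total cumulative consumption between the two groups". The main variable, under VARIABLES EVALUATED, is "pain intensity according to the NRS at different times: preoperative and at the 1st, 2nd, 12th and 24th postoperative hours": five readings per patient, four of them postoperative. No repeated-measures method is named anywhere. Under JUSTIFICATION OF SAMPLE SIZE, "a sample size calculation will be not performed".

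**The concern.** Kruskal-Wallis is a test for independent groups, and a Bonferroni post-hoc step has work to do only when there are three or more of them. The design has two groups. The only set of three or more levels within the main variable is the list of measurement times, and those readings come from the same patients.

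Two things are at stake. First, a test with no stated target can be placed after the data are seen. The most obvious multi-level placement, across NRS times, breaks the independence assumption and would hide real change over time. Second, the correction for multiple testing is attached to that test and not to the comparisons that answer the study question, namely anterior against posterior block at each postoperative time.

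**Working it through.** The plan gives no sample size, power, SD or correlation, so there is no figure of its own to reproduce.

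**Inputs from the document:** two groups (GOALS, PROTOCOL); NRS at five times, four postoperative (VARIABLES EVALUATED); threshold 0.05, sidedness not stated (STATISTICAL ANALYSIS PLAN).

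**Assumed inputs:** number of patients, NRS mean and SD, and an equal within-patient correlation ρ of 0.3 to 0.7 between any two times. Simulated NRS is rounded and limited to 0-10. Tests are two-sided.

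**1. Between the two blocks.** With k groups there are k(k−1)/2 pairs. For k = 2 that is one pair, so the Bonferroni factor is 1. In 200 simulated two-group data sets, the Kruskal-Wallis p-value differed from the Mann-Whitney p-value (normal approximation, no continuity correction) by at most 3 × 10⁻¹². The test is valid here but adds nothing.

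**2. Across the four postoperative times, no true change.** The variance of the difference between two time means on the same n patients is 2σ²(1−ρ)/n. A test for independent groups assumes 2σ²/n. The Kruskal-Wallis statistic therefore behaves roughly like (1−ρ) times a chi-square on 3 degrees of freedom, and the actual error is about P(χ²₃ > 7.815/(1−ρ)):

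| ρ | 7.815/(1−ρ) | Approximate error | Simulated, 40 patients | Simulated, 60 or 120 patients, 4 or 5 times |
|---|---|---|---|---|
| 0.3 | 11.16 | 1.1% | 1.3-1.6% | 1.0-1.4% |
| 0.5 | 15.63 | 0.14% | 0.2-0.3% | 0.1-0.3% |
| 0.7 | 26.05 | below 0.01% | 0.1% or less | about 0% |

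The Friedman test, which respects the pairing within patient, rejected in 4.4-5.5% of the same kind of data sets at every correlation tried.

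**3. What that costs in power.** With 60 patients, four times, SD 2 and a rise of 0.2 points per time (0, 0.2, 0.4, 0.6):

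| ρ | Kruskal-Wallis | Friedman |
|---|---|---|
| 0.3 | 17.3% | 30.7% |
| 0.5 | 10.5% | 42.4% |
| 0.7 | 5.7% | 64.3% |

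**4. The uncorrected group comparisons.** Four tests at 0.05, if independent, give 1 − 0.95⁴ = 18.5%. With the four test statistics correlated at 0.3 to 0.7, the family-wise error is about 17% falling to 13%. At 0.05/4 = 0.0125 each it is 1 − 0.9875⁴ = 4.9% if independent, and about 4-5% with correlation.

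**5. Price of the correction.** By normal approximation, 80% power at two-sided 0.05 means a standardised effect of 1.960 + 0.842 = 2.802. At 0.0125 the critical value is 2.498, so power is Φ(2.802 − 2.498) = Φ(0.304), about 62%.

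**The case against.** The text never says that Kruskal-Wallis will be used on the NRS times. It is an additional method, and the t or Mann-Whitney test at a single time uses one reading per patient, so repeated measurement does not invalidate it. The study also records independent factors with three levels: ease of technique, satisfaction, sensory block, and ASA status. Kruskal-Wallis with Bonferroni would be legitimate for comparing an outcome across those levels; in a simulation with 60 patients and three independent categories its error was 4.7%. The sizes above also rest on assumptions, and multiplicity across times would exist even if Kruskal-Wallis were never mentioned.

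Much of this stands, and it rules out three stronger readings that a reader might infer:

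- That the test has no valid use here. It is valid though redundant for two groups, and valid across three-level independent factors.
- That it will be run on the main variable. This is the natural multi-level reading, but it remains an inference.
- That each patient's readings will be pooled by group, with inflated false positives. Nothing in the plan suggests this, and two-group comparisons of continuous variables already have their own tests.

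The objection does not supply a target. No objective compares an outcome across levels of ease, satisfaction, sensory block or ASA status; the first three are outcomes and the last is an eligibility descriptor. Nor does it answer the fact that the plan's only correction sits on an unassigned test while the main comparisons have none.

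**Conclusion.** The point holds as a defect of specification with a real consequence for the main variable. The sentence has no stated target. It is redundant for the two-group comparison, and it would be far too conservative across the NRS times: about 1.5% to 0.1% actual error against a nominal 5% for ρ of 0.3 to 0.7. The direction does not depend on the assumed sample size, mean or SD; it follows from any positive within-patient correlation. The exact sizes do depend on the assumptions.

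The four postoperative group comparisons carry about 13-18% family-wise error as planned, on the same assumptions. The individual t or Mann-Whitney tests remain usable, so this should be corrected but does not by itself invalidate the study's main comparison.

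**What to change.** - Remove the Kruskal-Wallis sentence, or restrict it to a named outcome compared across a named factor with three or more independent patient groups.
- Analyse the four postoperative NRS readings with a mixed model: patient random effect; group, time and group-by-time as fixed effects; preoperative NRS as covariate. Report the group difference at each time from this model. If only change over time is wanted, Friedman with paired Wilcoxon tests is enough.
- Apply Holm or Bonferroni (0.0125 each) to the four postoperative between-group comparisons. Naming one primary time or one overall group test in advance would also control the error.

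**Cost:** analysis-plan wording only, using data already collected. The loss of power per comparison is more than slight: 80% becomes about 62% under Bonferroni, and Holm loses no more than that. This matters because no sample size was calculated. The change does not deal with allocation by anesthesiologist or with the unexplained pairing of the cohorts, which need separate attention.

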## BACKGROUND AND JUSTIFICATION OF THE PROJECT

Arthroscopic shoulder surgery is related to a high incidence of postoperative pain, being rated as intense by 45% of patients in the immediate postoperative period (1). The management of these patients can be complex due to the high incidence of preoperative pain and its variability during the postoperative period, which is higher in patients undergoing rotator cuff repair surgery (2).

It is crucial to ensure adequate postoperative pain control in this type of intervention, especially in the context of major outpatient surgery. Adequate postoperative pain control can have several benefits, such as reducing hospital stay (3), accelerating postoperative rehabilitation (4), and improving long-term outcomes (5).

The PROSPECT guideline for rotator cuff repair surgery recommends associating a regional analgesic technique with a multimodal pharmacological approach to pain. (6).

Traditionally, the interscalene block has been considered the gold-standard for analgesia in shoulder surgery; However, its possible serious complications limit its use. Currently, most anesthesiologists choose to perform more distal peripheral nerve blocks of the brachial plexus (upper trunk block, supraclavicular block, infraclavicular block at the costoclavicular level, axillary nerve block...) which, although highly effective, continue to cause impairment. prolonged motor activity and are not free of complications (phrenic paralysis, transient nerve injuries, inadvertent vascular punctures...) (7).

Shoulder anterior capsular block (SHAC) has recently been described. It is a fascial block of the anterior capsule of the shoulder that aims to avoid motor impairment while maintaining optimal analgesic efficacy (8)(9). However, so far only anatomical and descriptive studies of small case series have been published. Therefore, this research work, with the objective of comparing the postoperative analgesic effectiveness of two regional analgesic techniques: the SHAC block associated with the suprascapular nerve block performed anteriorly vs. suprascapular and axillary nerve blocks performed posteriorly in operated patients. of the shoulder via arthroscopic procedures that cause intense postoperative pain.

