## **STUDY HYPOTHESES**

Two analgesic strategies included within the usual clinical practice will be compared for postoperative pain control after shoulder arthroscopy. With this study we want to compare the ultrasound-guided block of the suprascapular nerves and the shoulder joint capsule via the anterior route versus the ultrasound-guided block of the suprascapular and axillary nerves via the posterior route.

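### The rationale for the new block is maintained analgesia, but the plan offers only difference tests at p < 0.05, without a between-group difference or confidence interval, so a non-significant pain result could not support that message

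*Combined protocol and SAP*

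**What the plan says.** **Rationale.** Background and Justification of the Project describes the SHAC block as one that "aims to avoid motor impairment while maintaining optimal analgesic efficacy". The same section then sets out the study "with the objective of comparing the postoperative analgesic effectiveness of two regional analgesic techniques".

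**Hypothesis.** Study Hypotheses says "Two analgesic strategies included within the usual clinical practice will be compared for postoperative pain control after shoulder arthroscopy". It gives no direction and no size of difference that would matter.

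**Outcome.** Under Variables Evaluated, "The main variable will be the measurement of pain intensity according to the NRS at different times": preoperatively and at 1, 2, 12 and 24 hours after surgery. No time point is named as primary. Motor block on arrival at the PACU is a secondary, two-level outcome.

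**Analysis.** The Statistical Analysis Plan summarises each group by mean and SD, by median and range, or by counts and frequencies. For continuous variables, "the results will be contrasted using the Student's T test if normality criteria will be met", and otherwise Mann-Whitney is used. Categorical variables go to chi-square or Fisher, and Kruskal-Wallis with Bonferroni is also mentioned. The only criterion is "assuming a p-value below 0.05 as significant".

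**Sample size.** Justification of Sample Size states that "a sample size calculation will be not performed". The recruitment section refers to an established number per group but does not give it.

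**The concern.** If the new block does what the background hopes, pain will be similar in the two groups and motor function better in the SHAC group. The planned analysis handles the pain half of that result worst. A test of difference can give evidence that the groups differ. When it fails to do so, it does not say how large a loss of analgesia remains compatible with the data. That requires the between-group difference and its confidence interval, and neither is planned for any outcome.

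The main favourable message could then rest on absence of evidence. Conversely, with a large caseload a trivial NRS difference could be reported as a finding because it crosses 0.05. The same gap affects infrequent complications, where a non-significant chi-square or Fisher test says little about the risk difference that can be excluded.

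**Working it through.** **Reproducing the plan.** There is no planned N, power, SD, effect size or margin to reproduce. The only figure is the 0.05 threshold, with sidedness unstated.

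**Assumptions (none from the documents).** Two equal groups; NRS compared at one time point; SD 2.0, 2.5 or 3.0; true worsening of 1 NRS point; two-sided t test at 0.05; 30, 50 or 100 patients per group.

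**Formulas.**
- Standard error of the difference: SE = SD × √(2/n).
- Noncentrality: δ = 1/SE, with 2n − 2 degrees of freedom.
- P(non-significant) = P(−t* < T < t*), where T is noncentral t with noncentrality δ and t* is the 97.5% point of the central t.
- 95% CI half-width = t* × SE.

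**One case in full: n = 30, SD 2.5.** SE = 2.5 × √(2/30) = 0.645. δ = 1/0.645 = 1.55. With 58 degrees of freedom t* = 2.002. P(non-significant) = 67%. Half-width = 2.002 × 0.645 = 1.29 points.

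**All cases: P(non-significant), with CI half-width in NRS points.**

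| n per group | SD 2.0 | SD 2.5 | SD 3.0 |
|---|---|---|---|
| 30 | 52% (1.03) | 67% (1.29) | 75% (1.55) |
| 50 | 30% (0.79) | 49% (0.99) | 62% (1.19) |
| 100 | 6% (0.56) | 20% (0.70) | 35% (0.84) |

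At 30 per group, even an observed difference of exactly zero would leave a 1-point worsening inside the interval at all three SDs. At 100 per group it would exclude that worsening at all three, but the plan as written would not report the interval that shows this.

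**Size needed if a formal claim were wanted.** Assume a 1-point margin, a true difference of 0, one-sided 0.025 and 80% power. Then n per group = 2 × SD² × (1.96 + 0.84)² / 1², rounded up: 63 (SD 2.0), 99 (SD 2.5) and 142 (SD 3.0). The margin is illustrative.

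**The case against.** The strongest reply is that the study never sets itself a non-inferiority question. The clause about maintaining efficacy describes what the technique is meant to achieve and does not name the posterior blocks as the reference. The study's own aim is an undirected comparison, for which a difference test is a natural choice. No section says that p above 0.05 will be taken as equality. This stands. A reader might infer that the protocol commits to an equivalence conclusion, but the documents do not support that.

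A reader might also infer that no effect can be estimated at all. That goes too far. From means, SDs and group sizes, or from counts, a reader can derive an unadjusted difference and its interval. This cannot be done reliably from median and range, which is the format prescribed whenever normality fails. Bounded pain scores and opioid doses given only on demand may well fail it.

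Nor do the documents show that the data will be too few. Recruitment is consecutive over 12 months in two hospitals, and nothing makes 30 per group likelier than 100. At 100 per group with SD 2.0, a 1-point loss is missed in only 6% of studies.

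Finally, imposing a non-inferiority test would bring its own problems. Allocation follows the responsible anesthesiologist, so an unadjusted interval inside a margin would not show maintained analgesia. Rescue opioid is triggered by the pain score, which can draw NRS values together and favour apparent similarity. No primary time point is named. These are good reasons not to require a margin by default. They are not reasons to omit the between-group difference and its interval.

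**Conclusion.** The concern holds as a mismatch between the stated rationale and the only decision rule. A p-value at or above 0.05 does not by itself show maintained analgesia at any sample size, and the plan provides no other between-group measure. Under the assumptions above, the risk that a true 1-point worsening goes undetected runs from 6% (100 per group, SD 2.0) to 75% (30 per group, SD 3.0). The range is wide because the documents give neither N nor SD, so the figures illustrate the problem and do not measure it in this study.

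Severity is SHOULD-FIX. No declared objective is contradicted and no data are lost, but the change is cheap and governs how the main result may be read.

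**What to change.** **In the Statistical Analysis Plan:**
- Report each comparison as a between-group difference with a 95% CI: mean or Hodges-Lehmann difference for NRS at each postoperative time and for opioid use; risk difference for motor block and adverse effects, with an exact interval when a count is zero.
- Adjust where possible for preoperative NRS and other recorded baseline factors, because allocation is by anesthesiologist.
- State that p ≥ 0.05 will not be read as equal analgesia.

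**Only if the investigators intend to claim maintained analgesia:** before analysis, fix a justified NRS margin and the time point to which it applies, and interpret the result together with rescue opioid use. Make the claim only if the interval excludes the margin, and otherwise report the result as inconclusive.

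**Cost.** The reporting change needs only SAP wording and analysis time, with no new data collection. The downside is that a small caseload may yield an inconclusive result. A formal claim costs more, since it needs enough patients: 63 to 142 per group under the illustrative assumptions above.
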